## 2. OBJECTIVES AND ENDPOINTS

Primary Objective	Primary Endpoint

 
To compare the pharmacokinetic properties of 300 mg ARN-75039 with excipients tablets (comparator) to 300 mg neat ARN-75039 in HPMC capsules (reference) following oral administration under fed conditions
 
	
 
PK parameters of 300 mg ARN-75039 with excipients tablets and 300 mg neat ARN-75039 in HPMC capsules, including but not limited to: 
 
Area under the plasma concentration-time curve from time zero to time of last quantifiable concentration (<math>AUC_{0-t}</math>).
 
Area under the plasma concentration-time curve from time zero to 24 hours post-dose (<math>AUC_{0-24}</math>).
 
Area under plasma concentration-time curve from time zero to infinity (<math>AUC_{0-\infty}</math>).
 
Maximum observed plasma concentration (<math>C_{max}</math>).
 
Minimum observed plasma concentration from time zero to 24 hours post-dose <math>C_{max0-24}</math>.
 
Time to reach <math>C_{max}</math> (<math>t_{max}</math>).
 
Half-life (<math>t_{1/2}</math>).
 
Apparent clearance after extravascular administration (CL/F).
 
Apparent volume of distribution during the terminal phase after extravascular administration (<math>V_z/F</math>).
 
 
 

Secondary Objectives	Secondary Endpoints

 
To provide additional information on the safety and tolerability of ARN-75039 administered orally in healthy participants.
 
	
 
Type and frequency of treatment-emergent adverse events (TEAEs).
 
Type and frequency of treatment-emergent serious adverse events (TESAEs).
 
Type and frequency of study drug-related >Grade 1 TEAEs.
 
Type and frequency of changes in clinical laboratory values, ECGs, colonic transit time (biomarker), physical examinations, and vital signs.
 

### 3. INVESTIGATIONAL PLAN

#### 3.1. Overall Study Design

ARN-75039-103 is a comparative, randomized, single-dose, crossover study to assess the PK, safety, and tolerability of neat ARN-75039 in hydroxypropyl methylcellulose (HPMC) capsules against ARN-75039 with excipients in tablet form administered by the oral route in healthy adult participants. The safety assessments will include standard evaluations of vital signs, clinical laboratory values, and ECGs.

Pharmacokinetic analysis of HPMC capsules filled with neat ARN-75039 was assessed in dogs under both fed and fasted conditions whereby capsules were filled with neat ARN-75039 relative to the dog's weight prior to dosing at the equivalent of a 10 mg/kg dose. Mean  $C_{max}$  and  $AUC_{0-24}$  were 5.2- and 8.8-fold higher in under fed conditions in dogs relative to fasted state conditions in dogs. Therefore, it was decided to dose participants in this study under fed state conditions.

Participants will be randomized into one of the following two sequences:

##### Sequence 1:

- Period 1: 300 mg neat ARN-75039 in HPMC capsules (reference product)
- Period 2: 300 mg ARN-75039 with excipients in tablet form (comparator)

##### Sequence 2:

- Period 1: 300 mg ARN-75039 with excipients in tablet form (comparator)
- Period 2: 300 mg neat ARN-75039 in HPMC capsules (reference product)

Written informed consent for study participation will be obtained before any study-related procedures or assessments are performed. All potential participants will be screened for potential participation, and those meeting all eligibility criteria will be offered participation in the study.

Participants will be admitted to the study site on the morning of Day -1, randomized to Period 1 study drug administration on Day 1, and will remain on site until study completion at Day 15. Participants will receive the randomized study drug in the morning following a meal. Participants will be dosed on Day 1 and Day 8 with a 7-day wash out period between the two dosing days. PK assessments will be performed according to the SOA ([Table 1](#)).

Participants that withdraw from active treatment or are terminated from the treatment period will undergo an Early Termination (ET) visit.

Participation in the study will be conducted in the following 5 defined periods, with a total study duration of approximately 57 days:

- **Screening Period:** The Screening Period begins when the informed consent form (ICF) is signed. During this period, participants will undergo baseline assessments to determine eligibility for study participation. The Screening Period duration will be up to 21 days; it will end after all evaluations required to meet eligibility have been completed. If a participant meets all eligibility criteria, they will be offered enrollment into the study.

- **Admission to the Study Center:** Participants will be admitted to the study site in the morning on the day prior to dosing of period 1 (Day -1) and will remain at the study site until study completion (Day 15). Upon admission to the study site, participants will be randomized into the study on Day 1 after the confirmation of eligibility.
- **Treatment Period:** This study consists of two treatment days separated by a 7-day washout period. The first treatment day will begin on Day 1 of Period 1 with administration of the first dose of study drug. The second treatment day will occur on the first day of Period 2 (Study Day 8). Following the dosing of the study drug on each treatment day, fifteen venous blood samples will be withdrawn via an indwelling cannula or by venipuncture at regular time intervals. Subjects will be discharged on Day 15.
- **End of Active Treatment (Day 15 Discharge Visit or Early Termination Visit):** Upon successful completion of active treatment, participants will be discharged from the study site on Day 15. The Day 15 Discharge Visit will include the completion of safety assessments, such as a physical examination, vitals, ECG recording, adverse event review, and clinical laboratory tests. Participants who complete both dosing days will be encouraged to complete all study visits. Participants who do not complete all study visits or terminate early from the study will be asked to complete the Early Termination Visit within 1 day after withdrawal from the study.
- **Day 36 Telephone Follow Up Phone Call:** Participants will be contacted by phone on Day 36—i.e., 28 days following the last study dose administered on Day 8. The purpose of this follow-up call is to assess for any adverse events.

If a participant has a study drug-related Grade > 1 TEAE during the Treatment Period, study drug dosing may be discontinued for that participant following discussion between the Investigator and Sponsor Medical Monitor. These participants will not be replaced. If a subject has a study drug-related Grade 1 TEAE during the Treatment Period, study drug dosing may also be discontinued for that subject per the Investigator's discretion. However, these subjects may be replaced at the Sponsor's discretion. Discontinued participants experiencing a study drug-related TEAE will be asked to complete follow up study visits through the Day 36 Phone Call Follow Up.

If a participant terminates early for a reason other than a study drug-related TEAE during the Treatment Period, the participant may be replaced. These participants will also be asked to complete follow up study visits through the Day 36 Phone Call Follow Up, unless they terminated their participation in the study prior to dosing. Study drug dose level modifications or dosing administration deviations outside the protocol-specified windows are not permitted during the Treatment Period.

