**Figure 1: Study Schema**

***Sequence 1***

***Sequence 2***

Participants will be randomized 1:1 into one of two sequences in this comparative, single dose, crossover study.

Participation in the study will be conducted in the following 5 defined periods:

- **Screening Period:** The Screening Period begins upon completion of the informed consent form (ICF). During this period, participants will undergo baseline assessments to determine eligibility

for study participation. The Screening Period duration will be up to 21 days; it will end after all evaluations required to meet eligibility have been completed. If a participant meets all eligibility criteria, they will be offered enrollment into the study.

- **Admission to Study Site:** Participants will be admitted to the study site in the morning on the day prior to dosing of period 1 (Day -1). Participants that are eligible to participate in the study and are randomized into the study will remain at the study site until completion of the treatment period (Study Day 15).
- **Treatment Period:** This study consists of two treatment days separated by a 7-day washout period. The first treatment day will begin on Day 1 of Period 1 with administration of the first dose of study drug. The second treatment day will occur on the first day of Period 2 (Study Day 8). Following the dosing of the study drug on each treatment day, fifteen venous blood samples will be withdrawn via an indwelling cannula or by venipuncture at regular time intervals.
- **End of Active Treatment (Day 15 Discharge Visit or Early Termination (ET) Visit):** Upon successful completion of active treatment, participants will be discharged from the study site on Study Day 15. The Discharge Visit will include the completion of safety assessments, such as a physical examination, vitals, ECG recording, adverse event review, and clinical laboratory tests. Participants who complete both dosing days will be encouraged to complete all study visits. Participants who do not complete all study visits or terminate from the study prior to Day 15 will be asked to complete the Early Termination Visit within 1 day after withdrawal from the study.
- **Day 36 Telephone Follow Up Phone Call:** Participants will be contacted by phone on Day 36—i.e., 28 days following the last study dose administered on Day 8. The purpose of this follow-up call is to assess for any adverse events.

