If a participant has a study drug-related Grade > 1 treatment-emergent adverse event (TEAE) during the Treatment Period, study drug dosing may be discontinued for that participant following discussion between the Investigator and Sponsor Medical Monitor. These participants will not be replaced. If a subject has a study drug-related Grade 1 TEAE during the Treatment Period, study drug dosing may also be discontinued for that subject per the Investigator's discretion. However, these subjects may be replaced at the Sponsor's discretion. Discontinued participants experiencing a study drug-related TEAE will be asked to complete follow up study visits through the Day 36 Phone Call Follow Up. If a participant terminates early for a reason other than a study drug-related TEAE during the Treatment Period, the participant may be replaced. These participants will also be asked to complete follow up study visits through the Day 36 Phone Call Follow Up, unless they terminated their participation in the study prior to dosing. Study drug dose level modifications or dosing administration deviations outside the protocol-specified windows are not permitted during the Treatment Period.

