**Table 1: Schedule of Assessments**

Procedure	Period	Screening Period	Admission	Period 1						Period 2								End of Active Treatment		Follow Up Phone Call
	Visit	Screening	P1D-1	P1D1	P1D2	P1D3	P1D4	P1D5	P1D6	P2D-1	P2D1	P2D2	P2D3	P2D4	P2D5	P2D6	P2D7	Discharge	ET	Day 36 +/- 2 days
	Study Day	Days -21 to -1	-1	1	2	3	4	5	6	7	8	9	10	11	12	13	14	15	ET a	
Informed consent		X																		
Eligibility criteria review		X	X																	
Randomization				X																
Demographics b		X																		
Medical and surgical histories		X	X																	
Vital signs c		X	X	X	X	X	X	X	X	X	X	X	X	X	X	X	X	X	X	
Physical examination d		X			X							X						X	X	
Pregnancy test e		X	X															X	X	
Concomitant medications		X	X															X	X	
Adverse events				X	X	X	X	X	X	X	X	X	X	X	X	X	X	X	X	X
12-lead ECG f		X	X	X	X	X	X			X	X	X	X	X				X	X	
Hematology g		X	X		X					X		X						X	X	

Procedure	Period	Screening Period	Admission	Period 1						Period 2								End of Active Treatment		Follow Up Phone Call
	Visit	Screening	P1D-1	P1D1	P1D2	P1D3	P1D4	P1D5	P1D6	P2D-1	P2D1	P2D2	P2D3	P2D4	P2D5	P2D6	P2D7	Discharge	ET	Day 36 +/- 2 days
	Study Day	Days -21 to -1	-1	1	2	3	4	5	6	7	8	9	10	11	12	13	14	15	ET a	
Drug test (urine) alcohol test (breath)		X	X																	
Serology h		X																		
Serum chemistry and coagulation g		X	X		X					X		X						X	X	
Urinalysis g		X			X							X						X	X	
Admission to site			X																	
Study drug administration				X							X									
PK (plasma) i				X	X	X	X	X	X	X	X	X	X	X	X	X	X	X	X	
Discharge from site																		X	X	

Abbreviations: D = Day(s); ECG = electrocardiogram; ET = early termination; HbsAg = hepatitis B virus surface antigen; HCV = hepatitis C virus; HIV = human immunodeficiency virus; min = minute(s); PK = pharmacokinetics.

- a If participant withdraws from the study prematurely, the ET visit is to be conducted within 1 days after withdrawal. Day 36 Follow Up Phone Call is also required for ET subjects.
- b Includes participant's sex, age, race, and ethnicity, as permitted by local privacy regulations.

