### 3.2. Justification for the Study Design

A randomized, comparative, crossover study was selected to eliminate participant variation and to improve precision of the PK characteristics of both study drug formulations with a smaller sample size. To compensate for the long half-life of the study drug and the relatively short washout period, additional PK timepoints were included to aid in modeling of the study drug clearance and elimination.

This clinical study is being performed in healthy participants to avoid interference with the results from disease processes and other drugs. Medications, substances, and food products that may interfere with the assessment of the PK profile of ARN-75039 are prohibited during study participation.

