## **6.10. Pharmacokinetics**

Fifteen venous blood samples will be withdrawn via an indwelling cannula or by venipuncture at regular time intervals. The exact date and time of PK sample collection is to be documented in the eCRF. Blood samples will be collected prior to and following administration of the single oral dose of neat ARN-75039 in HPMC capsules or ARN-75039 with excipients in tablet form at according to the timepoints listed in the SOA (Table 1). On Day 15 or at ET, the PK blood sample at approximately the same time as the dose of study drug was administered.

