#### **6.12.6. Adverse Events of Special Interest (AESI)**

All AEs and SAEs that occur during the study will be reported and investigated.

However, because of observations of tachycardia, early GI symptoms in animal studies (e.g., severe malnutrition due to reduced food consumption and body weight loss observed in rats that received ARN-75039 at doses  $\geq 2\times$  the NOAEL), and skin symptoms (e.g., grade 2 pruritus), subjects in this study should be monitored for any new onset or worsening of elevated heart rate, GI and skin-related signs and symptoms.

An AESI may be serious or nonserious (e.g., meeting regulatory criteria definition). Such events will require further investigation to better characterize and understand them. Even if not meeting the “seriousness” criteria to be reported as SAE, these events must be assessed for severity per [Section 6.13.3](#) and relationship to study drug similarly as for SAEs ([Section 6.13.2](#)).

Any AESI deemed as related (e.g., definitely, probably, or possibly), greater than grade 1 or severe (if not included in the NCI CTCAE) may require discontinuation of dosing of ARN-75039 (and follow-up until resolution) per the discretion of the Investigator and Sponsor Medical Monitor.

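### SAP 4.6 lets an AUC0-t cut short by early termination enter the 80–125% comparison; the protocol's Early Termination trigger also needs one consistent wording

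*Protocol*

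**What the plan says.** **Analysis.** SAP 4.6 takes AUC0-t by the trapezoidal method from time zero to the last observed concentration. Log AUC0-t, with Cmax and AUC0-∞, then goes into an ANOVA with treatment, period and sequence fixed and subject random within sequence. The 90% interval must lie within 80.00–125.00%, and the section accepts that the data may be unbalanced. SAP 4.1 admits anyone with at least one estimable PK parameter. Its profile exclusions are vomiting within 4 hours and, for the summary statistics, a pre-dose level above 5% of Cmax. In SAP 4.6 the 20% extrapolation limit, the three-point requirement and the adjusted R-squared check govern AUC0-∞ and the terminal-slope parameters, not AUC0-t. SAP 4.2 lists missed draws as deviations without giving them an analytic consequence.

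**When sampling can stop.** One paragraph of Protocol 3.1 reads: "Participants that withdraw from active treatment or are terminated from the treatment period will undergo an Early Termination (ET) visit". Later in 3.1, those who "terminate early from the study will be asked to complete the Early Termination Visit within 1 day after withdrawal from the study". The synopsis likewise refers to those who "terminate from the study prior to Day 15 will be asked to complete the Early Termination Visit". Footnote a of Table 1, repeated in the SAP, says: "If participant withdraws from the study prematurely, the ET visit is to be conducted within 1 days after withdrawal". The Early Termination (ET) column of Table 1 includes discharge from site, and Protocol 6.10 places one PK draw there: "On Day 15 or at ET, the PK blood sample at approximately the same time as the dose of study drug was administered".

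**After dosing stops.** The synopsis and 3.1 both say: "Discontinued participants experiencing a study drug-related TEAE will be asked to complete follow up study visits through the Day 36 Phone Call Follow Up". Neither lists the visits meant.

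**The concern.** A concentration–time profile that ends while drug is still measurable gives an AUC0-t over a shorter interval than the other profiles. Compared with a complete AUC0-t, it looks like lower exposure to whichever formulation was given, although it reflects only when sampling stopped. Protocol 3.2 indicates that the tail matters for this drug: "To compensate for the long half-life of the study drug and the relatively short washout period, additional PK timepoints were included". The SAP recognises the problem for AUC0-∞ and withholds that parameter when too much is extrapolated. It leaves AUC0-t from the same profile in one of the three comparisons that must meet the equivalence limits.

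The protocol wording is a separate and smaller matter. Dosing can stop without the participant leaving the study, so the two ET triggers can diverge. In that case no text says whether the remaining Period 1 PK, ECG and vital-sign time points are kept.

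**Working it through.** The documents give no figure for this effect, and the sample size of 16 has no statistical derivation (Protocol 3.3, SAP 3.3), so there is nothing to reproduce first.

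**Inputs from the documents.** 16 participants randomised 1:1 (8 + 8); sampling to 168 h (Table 1 footnote i); the ANOVA and the 20% limit in SAP 4.6.

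**Assumptions.** Half-life 24, 48 or 72 h (the protocol says only that it is long); within-subject correlation ρ of 0.5–0.9; mono-exponential decline with absorption and carry-over ignored; equal variances; ρ known.

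**Step 1: how much of AUC0-t survives.** The fraction captured relative to 168 h is [1 − 2^(−T/t½)] / [1 − 2^(−168/t½)], and the extrapolated share is 2^(−T/t½). For T = 48 h and t½ = 48 h these are 0.500/0.912 = 0.548 and 50%.

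**Step 2: weight of that value in the treatment estimate.**
- Both periods present: half of 1/8, so 1/16 = 0.0625 at any ρ.
- Period 1 only: (1 − ρ)/16, so 0.03125, 0.01875 and 0.00625 at ρ = 0.5, 0.7 and 0.9. It is not zero, because subject is a random effect in the SAP model.

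**Step 3: shift in the ratio**, exp(± weight × ln fraction) − 1. Cutting a tablet profile lowers the tablet/capsule ratio; cutting a capsule profile raises it. The Period 1-only column gives the upward shift.

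| Cut | t½ | Extrapolated | Fraction of AUC0-168 | Period 1 only, ρ 0.9 to 0.5 | Period 2, down / up |
|---|---|---|---|---|---|
| 24 h | 24 h | 50% | 0.504 | 0.43–2.16% | 4.19 / 4.38% |
| 24 h | 48 h | 71% | 0.321 | 0.71–3.61% | 6.85 / 7.35% |
| 24 h | 72 h | 79% | 0.257 | 0.85–4.33% | 8.13 / 8.85% |
| 48 h | 24 h | 25% | 0.756 | 0.18–0.88% | 1.73 / 1.76% |
| 48 h | 48 h | 50% | 0.548 | 0.38–1.89% | 3.68 / 3.83% |
| 48 h | 72 h | 63% | 0.462 | 0.48–2.44% | 4.72 / 4.95% |

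Every row exceeds 20% extrapolated, so AUC0-∞ would be withheld while AUC0-t stays in. Later cuts of a Period 2 profile matter less: 0.8–3.0% at 72 h, 0.4–1.8% at 96 h and at most 0.4% at 144 h. A profile with first-order absorption (0.8 per hour, assumed) on the actual sampling times gives similar fractions: 0.48, 0.31 and 0.25 at 24 h, and 0.75, 0.54 and 0.45 at 48 h.

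**Step 4: cost of excluding the value.** Per sequence, and up to a common factor, the variance of the period contrast is 2(1 − ρ)/n with n complete pairs, and (1 − ρ)²/8 + (1 − ρ²)/7 with seven pairs plus one Period 1-only value.
- Period 1-only value dropped, ρ = 0.5: √[(0.1429 + 0.1250)/(0.1384 + 0.1250)] = 1.008. At ρ = 0.9 it is 1.002.
- Period 2 value dropped, ρ = 0.5: √[(0.1384 + 0.1250)/0.2500] = 1.026. At ρ = 0.9 it is 1.033.

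**Step 5: the ET wording.** If ET and discharge did follow a stop in dosing, Table 1 footnotes c and i show what would be missed from Period 1. With ET on Day 2 it is 6 of 15 vital-sign and 6 of 17 PK time points (48–168 h), plus the 48 h and 72 h ECGs. On Day 4 it is 4 of each of the vital-sign and PK time points, and on Day 8 none.

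**The case against.** A reader might infer that the active-treatment sentence in Protocol 3.1 by itself ends follow-up of the Period 1 dose. The documents do not support that. The sentence adds a visit; it sets no clock, cancels nothing and does not mention discharge, and the paragraph before it keeps PK on the schedule of assessments. To reach early discharge, one must borrow the ET column of Table 1 while setting aside footnote a, which limits that column to study withdrawal. Participants whose dosing stops for a related event are asked to continue visits to Day 36. For related events of special interest above Grade 1, Protocol 6.12.6 also provides for follow-up tied to a stop in dosing ("and follow-up until resolution) per the discretion of the Investigator and Sponsor Medical Monitor"). The safety gap is therefore one of unnamed visits.

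The larger shifts, those for Period 2, also cannot come from a dosing-stop trigger, because both doses have been given by Day 8. They need a true study withdrawal. At half-lives of 48 and 72 h, the drug left at Day 8 would be 8.8% and 19.8% of the initial concentration, or about 8% and 17% of Period 2 Cmax (0.088/1.088 and 0.198/1.198). Both exceed the 5% limit in SAP 4.1, and carry-over would then be the larger problem. This stands as a limit on the upper end. It does not remove the point: SAP 4.1 applies the limit to summary statistics and does not clearly extend it to the ANOVA. At a 24 h half-life, where the limit is not reached, the Period 2 shift is still 1.7–4.4%.

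Finally, excluding every shortened AUC0-t would be too blunt. A Period 2 cut at 144 h shifts the ratio by at most 0.4%, yet excluding it costs 2.6–3.3% in standard error. That stands too, and the fix allows for it.

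**Conclusion.** The SAP gap is real and minor. Followed as written, SAP 4.6 puts an AUC0-t truncated by early termination into the 80.00–125.00% comparison while withholding AUC0-∞ from the same profile. One such profile cut at 24–48 h shifts the ratio by about 0.2–4.3% (Period 1 only) or 1.7–8.9% (Period 2). On the log scale the extremes are 0.042 and 0.085, against a margin of ln 1.25 = 0.223. These sizes rest on the assumed half-lives and correlations, and the Period 2 upper end also on ignoring carry-over. The documents give no basis for a case frequency. The gap exists however the ET trigger is read, because any study withdrawal after dosing can create it.

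The inconsistent trigger in Protocol 3.1 is a secondary wording fault. It leaves open which Period 1 assessments continue when only dosing stops; it does not show that follow-up would end early.

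**What to change.** **SAP 4.6, before analysis.** Flag and list any AUC0-t whose sampling ended early because of ET while concentrations were still quantifiable, in either period. Exclude it from the AUC0-t comparison if it fails a completeness limit fixed in advance, and keep Cmax from the same profile. Suitable limits are more than 20% extrapolated (the SAP's own figure), a last sample before a stated time such as 96 h, or a terminal slope that cannot be estimated. The choice depends on the half-life. At 72 h even a complete profile leaves 19.8% extrapolated and a 144 h cut leaves 25%, so the 20% limit would discard nearly complete profiles and a time limit would be gentler. The cost is one or two sentences, plus a standard error larger by 0.2–0.8% (Period 1 only) or 2.6–3.3% (Period 2) per excluded value.

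**Protocol 3.1 and synopsis.** Tie the ET visit to withdrawal from the study throughout. State that participants who only stop dosing complete the scheduled safety and PK assessments through 168 h after their last dose, and then the Day 36 call. This costs wording and up to about 5–6 bed-days per case (Day 3 or Day 2 to Day 8), within the stay already planned to Day 15. It helps only while dosing continues. SAP section 3 already describes randomisation in the past tense, so the SAP change is the one to secure.
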